**Notes:**

- All results outside predefined normal ranges will be flagged in the data listings.
- Repeat laboratory results within a visit will not be used in any summary calculations. Repeat results will be listed only.

**4.7.4.1 Non-inhibitory Anti-Drug Antibodies (ADAs)**

Non-inhibitory anti-drug antibodies (ADAs) screening test results and the confirmatory ADAs IgG and ADAs IgM test results will be tabulated by scheduled visit and inhibitor group. The percentages (positive or negative) at each visit will be based on the number of subjects who were tested at the visit. The final result will be positive if one of the confirmatory tests is positive; otherwise the final result will be negative. The final result over all visits will be based on the final assessment at EOS.

In addition, a shift analysis showing the change in status between baseline and anytime during the study, as well as between baseline and final assessment (EOS) will be provided.

The following information will be summarized, displaying the number and percentage of subjects:

- Positive anytime during the study
- Positive at baseline
- Positive at baseline and anytime after baseline
- Positive at baseline and at the end-of-study visit
- Negative at baseline and positive anytime post-baseline
- Negative at baseline and positive at the End-of-study Visit.

Baseline is the baseline visit of the current study.

Anti-rVIII antibody test results will be summarized for the Safety population overall and by age.

The relationship between ADA and inhibitor titer will be explored graphically overall and by subject displaying in a scatter plot inhibitor titer values along visits stratifying by ADA status.

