2.2.2.2 Safety

In **Arm 1 and Arm 3 (PTPs)**, the secondary safety endpoints are:

- Incidence of inhibitor formation to FVIII in at least 200 PTPs after 10 EDs and after 50 EDs with rVIII-SingleChain.
- Percentage of PTPs who develop antibodies against rVIII-SingleChain.
- Percentage of PTPs who develop antibodies to CHO proteins.

In **Arm 2 (PUPs)**, the secondary safety endpoints are:

- Incidence of high-titer inhibitor formation to FVIII (ie, inhibitor titer of ≥ 5 BU/mL) after 10 EDs with rVIII-SingleChain in PUPs.
- Incidence of low-titer inhibitor formation (ie, inhibitor titer of < 5 BU/mL) to FVIII after 10 EDs and after 50 EDs with rVIII-SingleChain in PUPs.
- Incidence of total (low- and high-titer) inhibitor formation to FVIII after 10 EDs and after 50 EDs with rVIII-SingleChain in PUPs.
- Percentage of PUPs who develop antibodies against rVIII-SingleChain.

- Percentage of PUPs who develop antibodies to CHO proteins.
- Percentage of PUPs with clinically significant abnormal values for blood pressure, or heart rate, or body temperature at 1, 2, 3, or 6 hours after the first rVIII-SingleChain injection.
- Percentage of PUPs with treatment-emergent clinically significant abnormal values for blood pressure, heart rate, or body temperature during the course of the study.

2.3

CCI [Redacted]

2.3.1

CCI [Redacted]

2.3.2

CCI [Redacted]

CCI [Redacted]

CCI

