### 3.5.6 Subgroups/Subpopulations

The following subgroups will be defined:

- Age based on age in this study:
  - For PTPs (Arm 1 and Arm 3): 0 to < 6 years,  $\geq 6$  to < 12 years,  $\geq 12$  to < 18 years and  $\geq 18$  to  $\leq 65$  years, 0 to <12 years,  $\geq 12$  to  $\leq 65$  years;
- By Region (Europe, US, Rest of the world, Asia)
- Japan subgroup

Efficacy endpoint will be analyzed by

- Positive vs. negative test for non-inhibitory Anti-Drug Antibodies (ADAs) during the Study.

The incidence of inhibitors will be summarized by

- Race (White, Black, Asian, and Other)

Annualized Bleeding Rates will be presented by

- ADA status (Positive and Negative)

For PUPs analyses for Annualized Bleeding Rates, hemostatic efficacy, TEAE and IR will be presented by inhibitor status (Positive and Negative) at the time of assessment.

CCI

Analyses by inhibitor status or inhibitor group have been defined in this SAP within relevant sections, the definition of inhibitor status and inhibitor group are the following ones:

*Inhibitor positive*

A subject is inhibitor positive if he developed a titre value (from the central lab) of at least 0.6 BU/mL, and was also confirmed in the next assessment with a titre value of at least 0.6 BU/mL.

*Inhibitor negative*

[figure not shown]
A subject is inhibitor negative if his titre value (from the central lab) was below 0.6 BU/mL.

*Inhibitor eradicated*

It refers to a subject who was previously documented with a confirmed inhibitor positive titre result and at a later point in the study, his titre value decreased and became low enough to classify him as inhibitor negative (titre value < 0.6 BU/mL). However, in order to become inhibitor eradicated, an inhibitor positive subject must first present an initial inhibitor negative titre result which must be confirmed in the next assessment by another inhibitor negative titre result.

*Inhibitor status*

A subject's inhibitor status represents a period in the study in which he is either inhibitor positive (+) or inhibitor negative (-), depending on his titre value at a given time.

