### AsBR

AsBR will be derived by inhibitor status and overall as follows:

$$(\text{number of bleeding events}) / (\text{observed treatment period of interest days}) * 365.25.$$

Only bleeding events requiring treatment will be included in the derivation of bleeding rates. The AsBR will be estimated for subjects who complete at least 8 weeks of treatment on the given inhibitor status using the subject's observed data. If the subject does not complete at least 8 weeks of treatment on the given inhibitor status, then the AsBR will be considered missing.

The number of spontaneous bleeding episodes per year based on a Poisson model and associated 95% CI and the number and percentage of subjects with zero bleeding episodes will be presented. In addition, the rate ratio of Prophylaxis modality to On-Demand modality (Prophylaxis- On-Demand) will be presented, along with the associated 95% CI, as obtained by the Poisson model.

Spontaneous bleeding episodes are those classified as 'Non-traumatic' in e-Diary or 'Spontaneous' in the eCRF. Annualized spontaneous bleeding rate will also be summarized for the following subgroup:

- Positive non-inhibitory Anti-Drug Antibodies (ADAs) and negative during the study
- Age based on age in this study: for PTPs: 0 to < 6 years,  $\geq 6$  to < 12 years,  $\geq 12$  to < 18 years and  $\geq 18$  to  $\leq 65$  years, 0 to <12 years,  $\geq 12$  to  $\leq 65$  years.
- Prophylaxis frequency: every second day, 3 times per week, 2 times per week, other regimen.

In these subgroup analyses rate ratio of Prophylaxis modality to On-Demand modality won't be displayed.

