## 4.11 Changes in Conduct or Planned Analyses from the Protocol

Section 2.1 and 2.2: In the protocol, incidence of inhibitor formation to FVIII in Arm 2, PUPs is stated that would be performed on at least 50 PUPs. However, this condition has been removed. Given that patients that develop inhibitors may be withdrawn from the study early, they would not necessarily achieve 50 exposure days but we would definitely have to include them in the calculation. Therefore the text was adjusted to ensure the option to properly report the endpoint regardless of these circumstances.

CCI

Section 3.5.3: Efficacy Population definition has been changed removing the exclusive inclusion of subjects who do not have an inhibitor at any time point during the study.

CCI

Section 4.6.1 and 4.6.2.1: In the Annualized Bleeding Rate analysis it has been added that subjects with an efficacy evaluation period less than 8 weeks (56 days) will be excluded from the analysis to exclude bias due to short evaluation period.

Section 4.6.2.2: The analysis of number of infusions of CSL627 required to achieve hemostasis has been added for completeness of analysis.

Section 4.7.1: Incidence of transient inhibitors has been added for completeness of analysis.

Section 4.7.2.1: Analysis of AESIs has been added for completeness of analysis.

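### The SAP's non-inhibitory antibody status is never checked against the inhibitor titer, so subjects with inhibitors can fall in either antibody group used for the bleeding-rate summaries

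*SAP*

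**What the plan says.** The protocol endpoint is neutral about the kind of antibody: "Percentage of PUPs who develop antibodies against rVIII-SingleChain" (Protocol 2.2.2.2, with a matching endpoint for PTPs). Inhibitors are identified separately, by the central laboratory's Nijmegen assay at 0.6 BU/mL or more (Protocol 8.6.1).

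SAP 4.7.4.1 analyses the antibody results under the name non-inhibitory ADA. Its rule is "The final result will be positive if one of the confirmatory tests is positive; otherwise the final result will be negative". Subjects with inhibitors are not left without a status: the results "will be tabulated by scheduled visit and inhibitor group", and a scatter plot shows "inhibitor titer values along visits stratifying by ADA status".

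That status then groups subjects for efficacy. SAP 3.5.6 lists "Positive vs. negative test for non-inhibitory Anti-Drug Antibodies (ADAs) during the Study" as an efficacy subgroup and names ADA status for the annualized bleeding rates. The AsBR part of SAP 4.6.1.1 repeats it: "Positive non-inhibitory Anti-Drug Antibodies (ADAs) and negative during the study". AsBR is a primary endpoint for PUPs.

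Protocol 11.2.3 restricts the Efficacy population to subjects without an inhibitor. SAP 3.5.3 does not, and SAP 4.11 records the change as "removing the exclusive inclusion of subjects who do not have an inhibitor".

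**The concern.** The label promises something the definition does not deliver. A subject is called non-inhibitory ADA positive without anyone looking at his titer, and the population restriction that would have kept inhibitor subjects out of the bleeding-rate tables has gone.

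Two outputs are affected. First, the difference in AsBR or ABR between antibody-positive and antibody-negative PUPs could reflect how inhibitor boys are spread over the two groups, and be read as an effect (or absence of effect) of non-neutralising antibodies. Second, the 4.7.4.1 counts of subjects positive at any time would be reported as non-inhibitory although they may include inhibitor cases.

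A related gap makes the grouping itself unclear. SAP 4.7.4.1 says "The final result over all visits will be based on the final assessment at EOS", whereas the subgroups in 3.5.6 and 4.6.1.1 refer to the whole study. A boy positive at month 6 and negative at the end of study could be placed in either group.

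**Working it through.** **Text check.** The plan gives no figure for the antibody comparison, so there is none to reproduce.

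1. The rule in SAP 4.7.4.1 has two inputs, IgG and IgM. Neither that section nor any other part of the SAP adds a titer condition.
2. The table by inhibitor group and the titer plot both require inhibitor-positive subjects to have an ADA status.
3. SAP 3.5.3 admits those subjects to the Efficacy population, on which AsBR and ABR are summarised.
4. SAP 4.6 and the AsBR text present PUP results by inhibitor status and overall. The ADA subgroup is listed afterwards, with no statement that it is crossed with inhibitor status.
5. Inhibitor status in SAP 3.5.6 is a period that can change within a subject. ADA status over the study reads as a fixed subject label. How the two combine is not defined.

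**Illustration of size.** From the documents: N = 24 PUPs (Protocol 11.1, SAP 3.9) and p = 35.4% inhibitor incidence (the study cited in Protocol 1.1), so 24 × 0.354 = 8.5 boys with an inhibitor and 15.5 without. Assumed, because the documents do not give them:

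- s, the probability that a boy with an inhibitor is ADA positive: 0 to 1
- q, the same probability for a boy without one: 0.1, 0.2 or 0.4
- k, the bleeding-rate ratio of inhibitor to no inhibitor: 0.5, 1.5, 2 or 3
- equal follow-up, and no effect of the antibody itself

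Formulas:

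- Inhibitor share of ADA positives: a = p·s / [p·s + (1−p)·q]
- Inhibitor share of ADA negatives: b = p·(1−s) / [p·(1−s) + (1−p)·(1−q)]
- Apparent positive-to-negative rate ratio: (a·k + 1 − a) / (b·k + 1 − b)

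Example with s = 0.5, q = 0.2, k = 2: positives are 8.5 × 0.5 = 4.2 with an inhibitor and 15.5 × 0.2 = 3.1 without, so a = 0.58. Negatives are 4.2 and 12.4, so b = 0.26. The ratio is 1.58 / 1.26, about 1.26.

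| s | Inhibitor share of ADA+ | Inhibitor share of ADA− | Apparent ratio at k = 2 |
|---|---|---|---|
| 0 | 0% | 38–48% | 0.68–0.73 |
| 0.25 | 26–58% | 31–41% | 0.89–1.20 |
| 0.5 | 41–73% | 23–31% | 1.07–1.40 |
| 0.75 | 51–80% | 13–19% | 1.27–1.59 |
| 1.0 | 58–85% | 0% | 1.58–1.85 |

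Ranges run over q. Across all the values of k the ratio spans 0.51 to 2.69. At k = 1 it is exactly 1, so the distortion needs inhibitor status to be related to bleeding rate.

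**The case against.** The strongest reply is that the SAP already separates inhibitor patients. SAP 4.6 makes presentation by inhibitor status a general rule for PUP efficacy, 3.5.6 repeats it for bleeding rates, and AsBR is derived that way in the section that holds the ADA subgroup. The by-visit ADA table is split by inhibitor group, so one column is free of inhibitor cases, and ADA results are listed for PUPs. The summary is also descriptive: Protocol 11.3 plans no p values, and no positive-to-negative rate ratio is specified.

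Much of this stands, and it limits the weight of the point. It does not remove it. Crossing the ADA tables with inhibitor status is a plausible reading of the general rule but is not stated. The overall column stays mixed in any case, and the positive-at-any-time counts are described overall and by age only.

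Three stronger readings are tempting and the documents do not support them:

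- *Boys with inhibitors will be in the positive group.* The documents do not describe the ADA assay or say that inhibitor samples test IgG or IgM positive. They could equally fall among the negatives.
- *The bias makes antibody-positive boys look worse.* The direction depends on s, q and k. The protocol is mixed even on k: the quoted text in 1.1 says an inhibitor leaves bleeding frequency unchanged, while 1.4 cites more bleeding complications.
- *Half to three quarters of the positive group are inhibitor patients.* Taking 8 inhibitor boys, all antibody positive, with 3 to 8 other positives gives 8/11 = 73% down to 8/16 = 50%. Both the full positivity and the 3 to 8 are assumptions, and Protocol 1.4 states that the absolute inhibitor risk with this product is unknown.

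**Conclusion.** The point holds as a definition and labelling gap with a real but unquantified effect. As written, non-inhibitory status is not conditional on the inhibitor result. Inhibitor subjects are in the Efficacy population, and they can sit in either antibody group for the AsBR and ABR summaries. The pooled comparison in PUPs is therefore open to confounding by inhibitor status in an unknown direction, and the any-time counts carry a label the rule does not justify.

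The illustrative ranges (inhibitor share of positives 0% to 85%, apparent ratio 0.51 to 2.69) rest on an external incidence and on assumed s, q and k. They show that the result depends on values the plan does not control; they do not forecast the trial. No formal test depends on this, so it is a change worth making rather than a threat to the primary analysis.

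**What to change.** In SAP 4.7.4.1, 3.5.6 and 4.6.1.1:

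- Report every confirmatory IgG or IgM positive as antibodies against rVIII-SingleChain (binding ADA), which is the protocol's endpoint.
- Reserve the term non-inhibitory for positives with a concurrent central-laboratory inhibitor titer below 0.6 BU/mL. Protocol 8.6.1 schedules both samples at the same visits.
- State that the ADA subgroup tables of AsBR and ABR in PUPs are crossed with inhibitor status, or shown for inhibitor-negative periods, and not only pooled.
- State whether a positive at any time or the end-of-study result defines the ADA subgroup.

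A concurrent titer is preferable to requiring that the subject was never confirmed inhibitor positive. The latter classifies by later outcome, discards a boy's earlier inhibitor-negative time, and conflicts with the time-varying status in SAP 3.5.6.

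The cost is wording and one derived flag from planned data, plus smaller cells. In the worked example the two antibody-positive cells hold about 4 and 3 boys, so some may be listed only under the SAP's rule for 3 or fewer patients, and the 8-week minimum per inhibitor status may thin them further.

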#### **4.7.4.2 Antibodies against Chinese Hamster Ovary cells**

Test results for antibodies against CHO cells will be summarized by reason for specimen collection. If more than one assessment has the same reason, then the most recent one will be considered. The number of subjects tested, and the results (positive or negative) will be displayed. The percentages (positive or negative) will be based on the number of subjects who were tested within reason.

In addition, to the results by reason for specimen collection a “final” result will be derived and presented. A subject’s final result will be counted as positive if the subject had a positive test at least once anytime during the study (i.e., at any time on or after screening, including at unscheduled visits). Otherwise, the “final” result will be negative.

The results for antibodies against CHO cells will be summarized also by Total EDs ranges based on first dose in the pivotal study (PTPs, Arm 1) or on first dose in this study (PTPs, Arm 3 and PUPs). According to the Total EDs they were exposed at time of assessment PTPs will be classified into 0-10 EDs, >10-15 EDs, >15-50 EDs, >50-75 EDs, >75-100 EDs, >100 EDs. PUPs will be classified into 0-10 EDs, >10-25 EDs, >25-50, and > 50 EDs. If more than one assessment is included in the same EDs range, then the most recent one will be considered. Definition of assessments at EDs=0 and handling of assessments done on the same date and time of a dose will be as detailed in [Section 4.7.1](#). Analysis will be repeated considering EDs achieved in the current study only.

The results for antibodies against CHO cells will be also summarized at the assessment of 10, 50 and 100 EDs in the current study as collected in the eCRF.

Tests for antibodies against CHO will be summarized for the total Safety population.

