- I:** Data will be acquired from the EOS visit from previous CSL-sponsored rVIII-SingleChain studies for inhibitors to FVIII, antibodies against rVIII-SingleChain and antibodies against CHO proteins for Day 1. Additional blood samples for inhibitors to FVIII and antibodies to rVIII-SingleChain and antibodies to CHO proteins will be collected at the closest visits after 10 EDs, after 50 EDs, and after 100 EDs. For the inhibitor blood samples, subjects should have a 4-day washout from last FVIII injection before blood draw if possible.
- J:** If the investigator collects blood samples for FVIII levels or inhibitor assessment at any other time during the study, the local laboratory results must be recorded in the eCRF and a duplicate sample must be submitted for analysis to the central laboratory (see [Section 8.6](#)).
- K:** Virology retention sample: CSL will retain a sample for 5 years from EOS.
- L:** rVIII-SingleChain may be dispensed at more frequent schedules if need is determined by the investigator.
- M:** Unused vials near expiration or with insufficient shelf life to cover time duration until next visit should be returned at the next scheduled visit. All unused vials will be returned at the EOS visit.
- N:** The observation period for adverse event (and serious adverse event) reporting in an individual subject will start at the time of giving written informed consent for participation in the current study and finish with the EOS visit. However, adverse events ongoing at the EOS visit will be followed until resolution or 28 days after the final administration of rVIII-SingleChain during this study, whichever is sooner.

Schedule of Assessments for Arm 2 PUPs With or Without Bleeding Episode at Screening and Assigned to PROPHYLAXIS

Assessments	Visits	Screening (Up to 28 days before Visit 1) ^A	Visit 1 ^A	Every month (± 7 days): Until 25 EDs achieved ^{B,C,D,E}	Every 3 months (± 7 days): From 25 EDs until EOS ^{B,C,D,E}	EOS ^E
Informed consent / assent		X				
Demographic information		X				
Medical and surgical history		X				
Review of inclusion / exclusion criteria; subject eligibility		X	X ^F			
Hemophilia A history (blood group, and gene defect)		X				
Hemophilia A social history and activity level		X	X	X	X	X
Review of prior medications (previous 28 days)		X				
Blood sample for gene defect, if no medical record ^G			← At any time during study ^G →			
Serum chemistry and hematology ^H		X		X	X	X
CD4 lymphocyte count (for HIV+ subjects) ^I		X				

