- M:** If not available in subject's medical records, FVIII activity level must be determined at Screening at the local laboratory, and the result must be available before enrollment.
- N:** Virology retention samples: At Visit 1, the sample must be taken before first rVIII-SingleChain injection. CSL will retain samples for 5 years from EOS.
- O:** At Visit 1, the investigator will administer first rVIII-SingleChain dose after screening assessments are completed and subject eligibility is confirmed. Subject must be observed at the clinic for at least 6 hours after dosing.
- P:** Switches to the on-demand regimen and between various prophylaxis regimens are allowed at any time at discretion of the investigator. The eCRF should be updated accordingly for each switch. Subjects **switching to on-demand** should maintain their originally assigned visit schedule.
- Q:** Unused vials near expiration or with insufficient shelf life to cover time duration until next visit should be returned at the next scheduled visit. All unused vials will be returned at the EOS visit.
- R:** The observation period for adverse event (and serious adverse event) reporting in an individual subject will start at the time of giving written informed consent for participation in the current study and finish with the EOS visit. However, adverse events ongoing at the EOS visit will be followed until resolution or 28 days after the final administration of rVIII-SingleChain during this study, whichever is sooner.

CCI

Schedule of Assessments for Arm 2 PUPs WITHOUT Bleeding Episode at Screening and Assigned to ON-DEMAND

Assessments	Visits	Screening (up to 28 days before Visit 1)	Visit 1	Follow-up visits 1 month (± 7 days) after each rVIII-SingleChain dose ^{A,C,E}	Monthly phone calls (± 7 days) if duration between visits is > 1 month ^{B,C,E}	EOS ^D
Informed consent / assent		X				
Review of inclusion / exclusion criteria; subject eligibility		X	X ^F			
Demographic information		X				
Medical and surgical history		X				
Hemophilia A history (blood group, gene defect)		X				
Hemophilia A social history and activity level		X	X	X		X
Review of prior medications (previous 28 days)		X				
Blood sample for gene defect ^G		← At any time ^G →				
Serum chemistry and hematology ^H		X		X		X
CD4 lymphocyte count (for HIV+ subjects) ^I		X				
Vital signs		X	X ^J	X		X
Physical examination		X		X		X
Body weight and height		X	X	X		X
Inhibitor to FVIII ^L		X ^K		X ^U		X

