- H:** Blood samples will be collected to assess IR and analyzed in the central laboratory. Subjects should have a 4-day washout after last FVIII injection before blood draws if possible. A pre-dose blood sample will be drawn. Subjects will then receive their prophylaxis dose of rVIII-SingleChain injection in the clinic. For on-demand subjects, the usual dose used to treat a bleeding episode or any other dose determined by the investigator will be administered in the clinic. A post-dose blood sample will be drawn 30 to 60 minutes (\pm 5 minutes) after injection. Incremental recovery will be collected at Day 1, at the closest visits after 10 EDs, after 50 EDs, and after 100 EDs (see [Section 8.6.2](#)).
- I:** Blood samples for inhibitors to FVIII, antibodies against rVIII-SingleChain, and antibodies to CHO proteins will be collected at Screening and at the closest visit after 10 EDs, after 50 EDs, and after 100 EDs. For the inhibitor blood samples, subjects should have a 4-day washout from last FVIII injection before blood draw if possible.
- J:** If the investigator collects blood samples for FVIII levels or inhibitor assessment at any other time during the study, the local laboratory results must be recorded in the eCRF and a duplicate sample must be submitted for analysis to the central laboratory (see [Section 8.6](#)).
- K:** Virology retention samples: The Visit 1 sample must be taken before first rVIII-SingleChain injection. CSL will retain samples for 5 years from EOS.
- L:** rVIII-SingleChain may be dispensed at more frequent schedules if need is determined by the investigator.
- M:** Unused vials near expiration or with insufficient shelf life to cover time duration until next visit should be returned at the next scheduled visit. All unused vials will be returned at the EOS visit.
- N:** The observation period for adverse event (and serious adverse event) reporting in an individual subject will start at the time of giving written informed consent for participation in the current study and finish with the EOS visit. However, adverse events ongoing at the EOS visit will be followed until resolution or 28 days after the final administration of rVIII-SingleChain during this study, whichever is sooner.

Schedule of Assessments for Surgery Substudy (Arms 1, 2 and 3)

Period	Before surgery	During Surgery	After Surgery
Body weight	X		
Hemoglobin measurement	X		X ^A
Predicted intraoperative estimated blood loss during surgery	X		

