8.10.2.1.1 Screening

For subjects presenting with a bleeding episode at Screening, it is anticipated that the Screening and Visit 1 assessments (ie, administration of first dose of rVIII-SingleChain and relevant efficacy assessments) may occur on the same calendar day due to the emergency nature of such presentation. The following procedures will be conducted and documented at Screening (within 28 days before Visit 1):

- Obtain written informed consent and assent of minors.
- Review of inclusion / exclusion criteria for Arm 2.
- Demographic information.
- Medical and surgical history.
- Hemophilia A history (blood group, and gene defect).
- Hemophilia A social history and activity level.
- Review of prior medications within the 28 days before Screening.
- Obtain blood sample for serum chemistry and hematology. Analyses should be determined at the local laboratory, and the results must be available before enrollment.
- Obtain blood sample for CD4 lymphocyte count (for HIV+ subjects; if the subject has received any blood components or per investigator discretion considering the subject's medical history).
- Vital signs.
- Physical examination.
- Record weight and height.
- Obtain blood sample for inhibitors to FVIII (analysis at central laboratory).
- Obtain blood sample for antibodies against rVIII-SingleChain and CHO proteins
- If FVIII activity level < 1% is not documented in subject's medical record: Obtain blood sample for plasma FVIII activity level and determine FVIII activity level at the local laboratory. The result must be available before enrollment.
- Review AEs.
- Review concomitant medications.

Subjects who complete all of these assessments and who fulfill all eligibility criteria for Arm 2 will be enrolled into the study. If the subject is not eligible for the study, the primary reason for screen failure must be entered in the eCRF.

8.10.2.1.2 Visit 1

The following procedures will be conducted and documented at Visit 1:

- If Screening and Visit 1 do not occur on the same calendar day:
Review inclusion / exclusion criteria and reconfirm subject eligibility.
- Obtain blood sample for gene defect if sample not previously obtained or gene defect not previously documented in medical records (Note: This sample should preferably be taken at Visit 1. If this is not possible, the sample can be taken at any time during the study).
- Obtain virology retention sample.
- Hemophilia A social history and activity level.
- Record weight and height.

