### 2.2.2 Secondary Safety Endpoints

The secondary Safety endpoints of the study are:

In **Arm 1 and Arm 3 (PTPs)**, the secondary safety endpoints are:

- Incidence of inhibitor formation to FVIII in at least 200 PTPs after 10 EDs and after 50 EDs with rVIII-SingleChain.
- Percentage of PTPs who develop antibodies against rVIII-SingleChain.
- Percentage of PTPs who develop antibodies to CHO proteins.

In **Arm 2 (PUPs)**, the secondary safety endpoints are:

- Incidence of high-titer inhibitor formation to FVIII after 10 EDs with rVIII-SingleChain in at least 50 PUPs.
  - A positive inhibitor is defined as two consecutive positive results ( $\geq 0.6$  Bethesda units (BU) /mL from the central lab.
  - The high-titer inhibitor is defined as any inhibitor tier of  $\geq 5$  BU/mL) during the study.
- Incidence of low-titer inhibitor formation (FVIII after 10 EDs and after 50 EDs with rVIII-SingleChain in at least 50 PUPs.

- The low-titer inhibitor is defined as any inhibitor tier of  $\geq 0.6$  and  $< 5$  BU/mL) during the study.
- Incidence of total (low- and high-titer) inhibitor formation to FVIII after 10 EDs and after 50 EDs with rVIII-SingleChain in at least 50 PUPs.
- Incidence of transient inhibitors (negative results within 6 months after diagnosis)
- Percentage of PUPs who develop antibodies against rVIII-SingleChain.
- Percentage of PUPs who develop antibodies to CHO proteins.
- Percentage of PUPs with clinically significant abnormal values for blood pressure, or heart rate, or body temperature at 1, 2, 3, or 6 hours after the first rVIII-SingleChain injection.
- Percentage of PUPs with treatment-emergent clinically significant abnormal values for blood pressure, heart rate, or body temperature during the course of the study.

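### The anti-CHO 'final' result counts a positive test from Screening, so a PUP positive only before the first dose would be counted towards the endpoint of antibodies developed

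*SAP*

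**What the plan says.** **Endpoint.** SAP 2.2.2, in line with Protocol 2.2.2.2, lists "Percentage of PTPs who develop antibodies to CHO proteins" and "Percentage of PUPs who develop antibodies to CHO proteins" as secondary safety endpoints.

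**Rule.** SAP 4.7.4.2 derives a 'final' anti-CHO result for each subject. It is positive "if the subject had a positive test at least once anytime during the study (i.e., at any time on or after screening", unscheduled visits included, and otherwise negative. Baseline status plays no part.

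**Sampling before dosing.**
- Arm 2: the Screening list in Protocol 8.10.2.1.1 includes "Obtain blood sample for antibodies against rVIII-SingleChain and CHO proteins", and the two on-demand schedules (8.10.2.2.1 and 8.10.2.3.1) do the same. At Visit 1 "the investigator will administer first rVIII-SingleChain dose after screening assessments are completed and subject eligibility is confirmed" (Arm 2 prophylaxis schedule, note O).
- Arm 3: "Blood samples for inhibitors to FVIII, antibodies against rVIII-SingleChain, and antibodies to CHO proteins will be collected at Screening" (Arm 3 schedule, note I), with Screening up to 28 days before Day 1.
- Arm 1: there is no Screening visit. For the Day 1 antibody values, "Data will be acquired from the EOS visit from previous CSL-sponsored rVIII-SingleChain studies" (Arm 1 schedule, note I).

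**Contrast.** For ADAs, SAP 4.7.4.1 plans a baseline shift analysis and a row for "Negative at baseline and positive anytime post-baseline". For inhibitors, SAP 4.7.1 estimates incidence only in subjects without an inhibitor at baseline.

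**The concern.** To develop an antibody is to acquire it after exposure. The 'final' rule instead measures whether a subject was ever positive, including on a sample drawn before exposure. A PUP who is reactive at Screening and negative at every later test would be 'final' positive although nothing changed on treatment.

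CHO is also the only one of the three immunogenicity endpoints whose analysis takes no account of baseline. SAP 4.11, which lists departures from the protocol, neither mentions nor justifies the rule. If the 'final' percentage is read as the endpoint, pre-existing reactivity is attributed to the product. In a group as small as Arm 2, one subject moves the percentage noticeably.

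**Working it through.** The documents state no anti-CHO rate, so there is no plan figure to reproduce. The check has two parts.

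**1. Does any other planned CHO summary isolate newly developed antibodies?**

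| Planned summary | What it shows | Links baseline to later status within a subject? |
|---|---|---|
| By reason for specimen collection (SAP 4.7.4.2) | Possibly Screening positives as their own row | No |
| By total-ED range (SAP 4.7.4.2, using the rules in 4.7.1) | Pre-dose tests are EDs = 0 and fall in the 0-10 class; only the latest test in a range is kept | No |
| At 10, 50 and 100 EDs (SAP 4.7.4.2) | Result at that assessment | No |
| By visit (Protocol 11.3.3.4.2) | Counts over subjects tested at the visit | No |
| 'Final' (SAP 4.7.4.2) | Ever positive from Screening on | No |

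Only the 'final' result gives one whole-study answer per subject, and none of the five conditions on a negative baseline.

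Eligibility does not remove the problem. Known or suspected hypersensitivity to CHO proteins is an exclusion in all arms (Protocol 4.1.2), but antibody positivity is not. The on-demand schedules for Arm 2 also allow the first dose before antibody results are back.

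**2. How far can the two definitions differ in Arm 2?**

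Let N be the number of PUPs, b the number positive before dosing and k the number negative at baseline and positive later.

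- SAP 'final' proportion = (b + k)/N
- Developed proportion = k/(N − b), taking every baseline-negative subject to have a later test

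N = 24 is the Arm 2 target in Protocol 11.1 and SAP 3.9 (sample size estimation). Values of b and k are assumptions. Brackets hold exact (Clopper-Pearson) 95% limits, added for scale only, since the SAP plans none for CHO.

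| b | k | SAP 'final' | Developed |
|---|---|---|---|
| 0 | 0 | 0/24 = 0% (0 to 14.2) | 0/24 = 0% (0 to 14.2) |
| 0 | 1 | 1/24 = 4.2% (0.1 to 21.1) | 1/24 = 4.2% (0.1 to 21.1) |
| 1 | 0 | 1/24 = 4.2% (0.1 to 21.1) | 0/23 = 0% (0 to 14.8) |
| 2 | 0 | 2/24 = 8.3% (1.0 to 27.0) | 0/22 = 0% (0 to 15.4) |
| 3 | 0 | 3/24 = 12.5% (2.7 to 32.4) | 0/21 = 0% (0 to 16.1) |
| 2 | 1 | 3/24 = 12.5% (2.7 to 32.4) | 1/22 = 4.5% (0.1 to 22.8) |

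With b = 0 the definitions agree. Otherwise each pre-dose positive adds 1/24 = 4.2 points to the 'final' result. SAP 2.2.2 and the planned-number part of 3.9 still refer to at least 50 PUPs; at that size each would add 1/50 = 2.0 points.

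The same calculation cannot be done by arm for PTPs, because the documents do not say how the 200 divide between Arms 1 and 3.

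**The case against.** **The SAP never names 'final' as the estimator of the endpoint.** True. It is offered in addition to the table by collection reason, and the protocol's own analysis is by visit. The link is an inference, but no other planned output yields a percentage of subjects with antibodies over the whole study.

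**Pre-dose positives need not be hidden.** Partly right. A Screening row may well appear in the table by reason, and the protocol's by-visit summary would show one. In the ED-range table, a later sample at or below 10 EDs replaces the Screening result, so the 0-10 class will often not contain it. What is missing is the within-subject link.

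**A reader might infer that the endpoint is overstated in all arms**, for example that 5% pre-dose reactivity among 200 PTPs would read as 5% with no new case. The documents do not support this.
- No pre-dose rate is given, so the 5% would be invented.
- Arm 1 subjects have already received rVIII-SingleChain when their entry value is taken. A positive there may be product-induced, and removing it could understate the endpoint. The SAP also does not say whether that value counts as on or after Screening.
- Arm 3 subjects may have had earlier rVIII-SingleChain (Protocol 3.1), so for them pre-dose means only before the first dose in this study.

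**The PTP analysis is finished.** The SAP's list of changes records the PTP study report as completed in November 2019. Only the PUP analysis can still be changed in advance.

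**Conclusion.** The point stands for Arm 2. As written, the rule counts a PUP who is positive only before the first dose as 'final' positive, in the only result that can serve the endpoint of antibodies developed. The size is 4.2 percentage points per such subject at n = 24, and nil if there are none. The endpoint could therefore be overstated; the documents do not show that it will be.

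In Arm 3 the same holds for positives before the first dose in this study, subject to possible earlier exposure. In Arm 1 the direction of any error is unknown, because the entry value follows exposure.

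The conclusion rests on reading 'final' as the endpoint's estimator, which is inferred from the absence of any alternative.

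**What to change.** **PUPs.** In SAP 4.7.4.2, define developed as negative at baseline (as defined in 4.1.1.4) and positive at any post-baseline test. Use as denominator the baseline-negative subjects with at least one post-baseline test; this also stops a subject never tested after baseline from being classed as negative by default. Show baseline-positive subjects in separate rows, following the ADA categories in 4.7.4.1. Record the change in 4.11.

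**PTPs.** Give the same table as a supplement to the completed report, by arm, with the baseline stated. For Arm 1, report entry-positive subjects separately, and call them neither pre-existing nor newly developed unless a result from before the lead-in study exists. The documents do not say whether such results are available.

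**Cost.** For PUPs, a few lines of SAP text and one programming flag, using samples already scheduled, with a slightly smaller denominator. For PTPs, one supplementary table.
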